6.2.3.2 Biomarker Research

In addition to the MMR and MGMT markers, and the longitudinal mutational burden determination, which are an inherent component for the enrichment strategy of the trial, the following potential markers of pembrolizumab pharmacodynamics will be considered:

Analysis of PD-L1 and PD1 expression in TRIAL Phase eligible patients:

- PD-L1 will be measured on archival or newly obtained core or excisional biopsies by centralized IHC using QualTeck assay and 22C3 antibody clone (Merck). Positivity is defined as membranous PD-L1 expression in > 1% of cells in tumor and stroma.
- PD1 and other lymphocyte activation markers will be measured in peripheral blood lymphocyte (PBL) post-treatment, and correlated with mutational load. PBL will be collected at baseline and with each treatment. PBL are isolated and stored frozen until use.

Investigation of the immunomodulatory effect of TMZ:

We plan to explore also the association of PD-1 positivity, and tumor infiltrating lymphocyte characteristics with clinical responses to subsequent Pembrolizumab treatment. In such cases archived tumor tissues and tissue obtained at biopsy will be compared. Archival and post-TMZ tumor biopsies will be analyzed for PD-1/PD-L1 expression as well as for a variety of potential immune-markers as described in 9.1.4.2.

7.0 METHODOLOGY

7.1 Entry Criteria

Patient selection criteria are progressively restrictive according to the 3-step selection strategy of the trial and are reported separately for each phase.

7.1.1 Entry criteria for SCREENING Phase

1. Histologically confirmed diagnosis of metastatic colorectal cancer.

2. Documented RAS extended mutations in the archival sample (cohort P only).
3. ECOG performance status 0-1.
4. SCREENING phase informed consent signed.
5. Understanding and accepting the need for undergoing two tumor biopsies if eligible for PRIMING Phase.
6. Age \geq 18 years.
7. Availability of all diagnostic FFPE blocks (primary tumor and or metastases), or at least 20 slides (primary tumor and/or metastases). Formalin-fixed, paraffin embedded (FFPE) tissue blocks are preferred to slides.
8. Normal organ functions (see Table 7.1.4 below).

7.1.2 Entry Criteria for PRIMING Phase

Participants are eligible to be included in the PRIMING Phase, only if all of the following criteria apply:

1. Fulfilment of all the SCREENING inclusion criteria;
2. PRIMING informed consent signed;
3. Confirming the willingness to undergo two tumor biopsies,
4. Acceptance that if the mutational load determination is unfeasible for technical reasons (not enough tissue, substandard test performance, etc.), access to TRIAL phase will not be possible.
5. Imaging documented failure of previous standard CRC therapies including fluoropyrimidine, oxaliplatin, irinotecan plus or minus antiangiogenics agents (Bevacizumab, Aflibercept, Regorafenib, others).
6. At least one measurable tumor lesion as per RECIST v1.1. Lesions in previously irradiated areas or those that have received other loco-regional therapies (i.e. percutaneous ablation) should not be considered measurable unless there is clear documented evidence of progression of the lesion since therapy. Imaging must be performed maximum within 28 days prior to enrolment.
7. ECOG performance status 0 or 1;
8. Following results in the SCREENING Phase tests:
 - Proficient MMR status assessed by IHC or MSI-low status defined by PCR (Bethesda panel);
 - Negative score for the MGMT protein expression IHC test;
 - Positive score for the MGMT promoter methylation performed on tissue.
9. Women with childbearing potential should complete a pregnancy test and be willing to use highly effective contraceptive methods.
10. Normal organ functions as defined in the Table 7.1.4 below.

7.1.3 Entry Criteria for TRIAL Phase

1. Fulfilment of all the SCREENING inclusion criteria and deficient MMR status (IHC) or MSI-High status (PCR) (cohort D only).
2. Fulfilment of all the SCREENING and PRIMING inclusion criteria (cohort P only).
3. TRIAL Phase informed consent signed (both cohorts).
4. Imaging documented PD to TMZ (cohort P only).
5. A mutational load value ≥ 20 mutations/MB at TMZ-ML assay (cohort P only).
6. Imaging documented failure of previous standard CRC therapies including fluoropyrimidine, oxaliplatin, irinotecan plus or minus targeted agents (Bevacizumab, Aflibercept, Regorafenib, Cetuximab, Panitumumab, others) (cohort D only).
7. At least one measurable tumor lesion as per RECIST v1.1. Lesions in previously irradiated areas or those that have received other loco-regional therapies (i.e. percutaneous ablation) should not be considered measurable unless there is clear documented evidence of progression of the lesion since therapy. Imaging must be performed maximum within 28 days prior to enrolment (both cohorts).
8. Women with childbearing potential should complete a pregnancy test and be willing to use highly effective contraceptive methods (both cohorts).
9. Normal organ functions as defined in the Table 7.1.4 below. Blood specimens must be collected within 10 days prior to the start of study treatment.

7.1.4 Adequate Organ Function Laboratory Values

System	Laboratory Value
Hematological	
Absolute neutrophil count (ANC)	$\geq 1500/\mu\text{L}$
Platelets	$\geq 100.000/\mu\text{L}$
Hemoglobin	$\geq 9.0 \text{ g/dL}$ or $\geq 5.6 \text{ mmol/L}^a$
Renal	
Creatinine OR Measured or calculated ^b creatinine clearance (GFR can also be used in place of creatinine or CrCl)	$\leq 1.5 \times \text{ULN}$ OR $\geq 30 \text{ mL/min}$ for participant with creatinine levels $> 1.5 \times \text{institutional ULN}$
Hepatic	
Total bilirubin	$\leq 1.5 \times \text{ULN}$ OR direct bilirubin $\leq \text{ULN}$ for participants with total bilirubin levels $> 1.5 \times \text{ULN}$
AST (SGOT) and ALT (SGPT)	$\leq 2.5 \times \text{ULN}$ ($\leq 5 \times \text{ULN}$ for participants with liver metastases)
Coagulation	
International normalized ratio (INR) OR prothrombin time (PT)	$\leq 1.5 \times \text{ULN}$ unless participant is receiving anticoagulant therapy as long as PT or aPTT is within therapeutic range of intended use of anticoagulants
Activated partial thromboplastin time (aPTT)	

ALT (SGPT)=alanine aminotransferase (serum glutamic pyruvic transaminase); AST (SGOT)=aspartate aminotransferase (serum glutamic oxaloacetic transaminase); GFR=glomerular filtration rate; ULN=upper limit of normal.

^a Criteria must be met without erythropoietin dependency and without packed red blood cell (pRBC) transfusion within last 2 weeks.

^b Creatinine clearance (CrCl) should be calculated per institutional standard.

Note: This table includes eligibility-defining laboratory value requirements for treatment; laboratory value requirements should be adapted according to local regulations and guidelines for the administration of specific therapies.

7.2 Exclusion Criteria

Participants are excluded from the study if any of the following criteria apply:

1. A woman of child bearing potential who has a positive serum pregnancy test within 72 hours prior to allocation (see Appendix 3).
2. Has received prior therapy with an anti-PD-1, anti-PD-L1, or anti-PD-L2 agent or with an agent directed to another stimulatory or co-inhibitory T-cell receptor (eg, CTLA-4, OX-40, CD137).
3. Has received prior systemic anti-cancer therapy including investigational agents within 4 weeks [could consider shorter interval for kinase inhibitors or other short half-life drugs] prior to enrollment.
 - a. Note: Participants must have recovered from all AEs due to previous therapies to \leq Grade 1 or baseline. Participants with \leq Grade 2 neuropathy may be eligible.
 - b. Note: If participant received major surgery, they must have recovered adequately from the toxicity and/or complications from the intervention prior to starting study treatment.
4. Has received prior radiotherapy within 2 weeks of start of study treatment (with Pembrolizumab). Participants must have recovered from all radiation-related toxicities, not require corticosteroids, and not have had radiation pneumonitis. A 1-week washout is permitted for palliative radiation (≤ 2 weeks of radiotherapy) to non-CNS disease.
5. Has received a live vaccine within 30 days prior to the first dose of study drug. Examples of live vaccines include, but are not limited to, the following: measles, mumps, rubella, varicella/zoster (chicken pox), yellow fever, rabies, and typhoid vaccine. Seasonal influenza vaccines for injection are generally killed virus vaccines and are allowed; however, intranasal influenza vaccines (eg, FluMist®) are live attenuated vaccines and are not allowed.
6. Is currently participating in or has participated in a study of an investigational agent or has used an investigational device within 4 weeks prior to the first dose of study treatment.

- a. Note: Participants who have entered the follow-up phase of an investigational study may participate as long as it has been 4 weeks after the last dose of the previous investigational agent.
7. Has a diagnosis of immunodeficiency or is receiving chronic systemic steroid therapy (in dosing exceeding 10 mg daily of prednisone equivalent) or any other form of immunosuppressive therapy within 7 days prior to the first dose of study drug.
8. Has a known additional malignancy that is progressing or has required active treatment within the past 3 years. Note: Participants with basal cell carcinoma of the skin, squamous cell carcinoma of the skin, or carcinoma in situ (e.g. breast carcinoma, cervical cancer in situ) that have undergone potentially curative therapy are not excluded.
9. Has known active CNS metastases and/or carcinomatous meningitis. Participants with previously treated brain metastases may participate provided they are radiologically stable, i.e. without evidence of progression for at least 4 weeks by repeat imaging (note that the repeat imaging should be performed during study screening), clinically stable and without requirement of steroid treatment for at least 14 days prior to first dose of study treatment.
10. Has severe hypersensitivity (\geq Grade 3) to pembrolizumab and/or any of its excipients.
11. Has severe hypersensitivity (\geq Grade 3) to temozolomide and/or any of its excipients.
12. Has active autoimmune disease that has required systemic treatment in the past 2 years (i.e. with use of disease modifying agents, corticosteroids or immunosuppressive drugs). Replacement therapy (eg., thyroxine, insulin, or physiologic corticosteroid replacement therapy for adrenal or pituitary insufficiency, etc.) is not considered a form of systemic treatment.
13. Has a history of (non-infectious) pneumonitis that required steroids or has current pneumonitis.
14. Has an active infection requiring systemic therapy.
15. Has a known history of Human Immunodeficiency Virus (HIV). Note: No HIV testing is required.
16. Has a known history of Hepatitis B (defined as Hepatitis B surface antigen [HBsAg] reactive) or known active Hepatitis C virus infection. Note: no testing for Hepatitis B and Hepatitis C is required unless mandated by local health authority.
17. Has a known history of active TB (Bacillus Tuberculosis).
18. Has a history or current evidence of any condition, therapy, or laboratory abnormality that might confound the results of the study, interfere with the subject's participation for the full duration of the study, or is not in the best interest of the subject to participate, in the opinion of the treating investigator.
19. Has known psychiatric or substance abuse disorders that would interfere with cooperation with the requirements of the trial
20. Is pregnant or breastfeeding, or expecting to conceive or father children within the projected duration of the study, starting with the screening visit through 120 days after the last dose of trial treatment.

7.2.1 Lifestyle Restrictions

7.2.1.1 Meals and Dietary Restrictions

Participants should maintain a normal diet unless modifications are required to manage an AE such as diarrhea, nausea or vomiting.

7.2.1.2 Contraception

ICH M3 guidance requires precautions to be taken to minimize risk to fetus or embryo when including women of childbearing potential in clinical studies.

Temozolomide and Pembrolizumab may have adverse effects on a fetus in utero. Refer to Appendix 3 for approved methods of contraception.

7.2.2 Pregnancy

If a participant inadvertently becomes pregnant while on treatment with Temozolomide or pembrolizumab, the participant will be immediately discontinued from study treatment. The site will contact the participant at least monthly and document the participant's status until the pregnancy has been completed or terminated. The outcome of the pregnancy will be reported to delegated pharmacovigilance and to Merck Global Safety according to timelines as defined in section 9.2.3 if the outcome is a serious adverse experience (e.g., death, abortion, congenital anomaly, or other disabling or life-threatening complication to the mother or newborn). The study Investigator will make every effort to obtain permission to follow the outcome of the pregnancy and report the condition of the fetus or newborn to Merck. If a male participant impregnates his female partner, the study personnel at the site must be informed immediately and the pregnancy must be reported to delegated pharmacovigilance and to Merck Global Safety followed as described in section 9.2.3.

7.2.3 Use in Nursing Women

It is unknown whether pembrolizumab is excreted in human milk. Since many drugs are excreted in human milk, and because of the potential for serious adverse reactions in the nursing infant, participants who are breast-feeding are not eligible for enrollment.

7.3 Trial Treatments

Only qualified personnel familiar with procedures that minimize undue exposure to themselves and to the environment should undertake the preparation, handling, and safe disposal of chemotherapeutic agents.

The treatment to be used in this trial is outlined below in Table 7.3.

Table 7.3 Trial Treatment

Drug	Dose/Potency	Dose Frequency	Route of Administration	Regimen/Treatment Period	Use
Temozolomide	150 or 200 or 100 mg/m ² (7.3.1.2)	Q4W	P.O.	Days 1-5 every 28 days (PRIMING Phase)	Experimental
Pembrolizumab	200 mg	Q3W	IV infusion	Day 1 of each 3 week cycle (TRIAL Phase)	Experimental

Trial treatment should begin as close as possible to the date on which treatment is allocated/assigned.

7.3.1 Temozolomide - Dose Selection/Modification

7.3.1.1 Dose Selection

The rationale for selection of doses to be used in this trial is provided in section 6.2.2 Justification for Dose.

7.3.1.2 Temozolomide-Dose modification (Escalation/Titration/Other)

The starting dose of TMZ is 150 mg/sq/day. The dose can be modified at the start of cycle 2. During treatment, a complete blood count should be obtained on Day 22 (21 days after the first dose of TMZ). According to day 22 CBC results and non-haematological toxicity observed during cycle 1 the dose of TMZ remain 150 mg/sq/day, or is modified as reported below.

Table 7.3.1.2 Temozolomide - Dose modification

Toxicity	Temozolomide 2 nd cycle dose		
	Increase dose to 200 mg/sq/day	Reduce dose to 100 mg/sq/day	Discontinue TMZ
Absolute Neutrophil Count day 22 cycle 1	$\geq 1.5 \times 10^9/L$,	$< 1.0 \times 10^9/L$	Na
Thrombocyte Count	$\geq 100 \times 10^9/L$.	$< 50 \times 10^9/L$	Na
CTC Non-Hematologic toxicity (except for alopecia, nausea, vomiting)	Grade ≤ 2 (except for alopecia, nausea and vomiting),	CTC Grade 3	CTC Grade 4

In the event of multiple toxicities, dose modifications should be applied based upon the most severe toxicity observed.

7.3.1.3 Patients with hepatic or renal impairment

The pharmacokinetics of TMZ are comparable in patients with normal hepatic function and in those with mild or moderate hepatic impairment. No data are available on the administration of TMZ in patients with severe hepatic impairment (Child's Class C) or with renal impairment. Based on the pharmacokinetic properties of TMZ, it is unlikely that dose reductions are required in patients with severe hepatic impairment or any degree of renal impairment. However, caution should be exercised when TMZ is administered in these patients.

7.3.1.4 Elderly patients

Based on a population pharmacokinetic analysis in patients 19-78 years of age, clearance of TMZ is not affected by age. However, elderly patients (> 70 years of age) appear to be at increased risk of neutropenia and thrombocytopenia.

7.3.1.5 Contraindications to Temozolomide treatment

- Hypersensitivity to the active substance or to any of the excipients.
- Hypersensitivity to dacarbazine (DTIC).
- Severe myelosuppression.

Note: For warnings see the Temozolomide SmPC.

7.3.1.6 TMZ-Timing of dose administration

Temozolomide will be administered orally once daily at the dose of 150-200 mg/m²/day for 5 consecutive days of each treatment cycle (see 7.3.1.2). A treatment cycle will comprise 5 days of Temozolomide administration (Day 1 to 5) followed by 23 days of rest for a total of 28 days (4 weeks) period (dose-schedule: 150 mg/m² day 1-5 q28). After an overnight fasting, with free access to water, patients will take the study drug with a large glass of plain water without ice. A light breakfast can be served 1.5-2 hours after study drug intake.

Dose modification should be implemented according to recommendations detailed in section 7.3.1.2.

Each patient will remain on treatment until PD unless patient refusal, consent withdrawal, or the occurrence of unacceptable toxicity.

The site personnel handling the study medication to patients must ensure that they fully understand that the treatment period (cycle) comprises 28 days, consisting of 5 days of daily administration, followed by a 23-day resting period, from Day 6 to Day 28. During each treatment cycle, extension of treatment period to Days >5 is not allowed, even in case of missed doses.

Additionally, the patients should be informed:

- to take the study drug in fasting state.
- to swallow the capsules whole with a glass of plain water without ice; capsules must not be opened or chewed; water is allowed during fasting period.
- to take the study drug at the same time each day (1.5-2 hours before breakfast).
- if the patient forgets to take the study drug at the usual time, to take it between meals at any time during the same day and record the event.
- if the patient misses one day, to take the normal amount the next day, if scheduled. Not to double the daily prescribed dose of the study drug and to track the number of capsules missed and the reason for it.
- if vomiting occurs during or after having taken the daily dose, not to take extra capsules that day and to take the normal amount the next day, if scheduled. Not to double the daily prescribed dose of the study drug and record the event to adhere to the principles of safe handling and storage of the study medication.
- Breaking/crushing or opening the capsules must be avoided. In such cases, record of the broken capsules should be kept. In case of opening of the capsules, to avoid contact or inhalation. In case of skin contact, to wash the affected area with plenty of water or soap and water. In case of eye-contact, to rinse thoroughly with plenty of water and see medical advice as soon as possible.
- To return all packaging as well as not-taken capsules (if applicable) to the site personnel.

As much of this information as possible should first be given at the pre-treatment visit and reinforced on subsequent visits. A diary of TMZ assumption must be given to the patient every treatment cycle and the correct compilation must be revised by the investigator.

7.3.1 Pembrolizumab - Dose Selection/Modification

7.3.1.1 Dose Selection

The rationale for selection of doses to be used in this trial is provided in section 4.0– Background and Rationale.

7.3.2 Timing of Dose Administration

Trial treatment should be administered on Day 1 of each cycle after all procedures/assessments have been completed as detailed on the Trial Flow Chart (section 6.0).

- Pembrolizumab 200 mg will be administered on an outpatient basis as a 30 minute IV infusion every 3 weeks. Sites should make every effort to target infusion timing to be as close to 30 minutes as possible. However, given the variability of infusion pumps from site to site, a window of -5 minutes and +10 minutes is permitted (i.e., infusion time is 30 minutes: -5 min/+10 min).
- Pembrolizumab may be administered up to 3 days before or after the scheduled Day 1 of each cycle due to administrative reasons.

7.3.2 Dose Modification and toxicity management for immune-related AEs associated with pembrolizumab

AEs associated with pembrolizumab exposure may represent an immunologic etiology. These immune-related AEs (irAEs) may occur shortly after the first dose or several months after the last dose of pembrolizumab treatment and may affect more than one body system simultaneously. Therefore, early recognition and initiation of treatment is critical to reduce complications.

- Based on existing clinical study data, most irAEs are reversible and could be managed with interruptions of pembrolizumab, administration of corticosteroids and/or other supportive care.
- For suspected irAEs, ensure adequate evaluation to confirm etiology or exclude other causes. Additional procedures or tests such as bronchoscopy, endoscopy, skin biopsy may be included as part of the evaluation. Based on the severity of irAEs, withhold or permanently discontinue pembrolizumab and administer corticosteroids.
- Dose modification and toxicity management guidelines for irAEs associated with pembrolizumab are provided in Table 7.3.2.

Table 7.3.2 Dose modification and toxicity management guidelines for immune-related AEs associated with pembrolizumab

General instructions:				

 1. Corticosteroid taper should be initiated upon AE improving to Grade 1 or less and continue to taper over at least 4 weeks. 2. For situations where pembrolizumab has been withheld, pembrolizumab can be resumed after AE has been reduced to Grade 1 or 0 and corticosteroid has been tapered. Pembrolizumab should be permanently discontinued if AE does not resolve within 12 weeks of last dose or corticosteroids cannot be reduced to ≤ 10 mg prednisone or equivalent per day within 12 weeks. 3. For severe and life-threatening irAEs, IV corticosteroid should be initiated first followed by oral steroid. Other immunosuppressive treatment should be initiated if irAEs cannot be controlled by corticosteroids. 				
Immune-related AEs	Toxicity grade or conditions (CTCAEv4.03)	Action taken to pembrolizumab	irAE management with corticosteroid and/or other therapies	Monitor and follow-up
Pneumonitis	Grade 2	Withhold	
 • Administer corticosteroids (initial dose of 1-2 mg/kg prednisone or equivalent) followed by taper 	
 • Monitor participants for signs and symptoms of pneumonitis • Evaluate participants with suspected pneumonitis with radiographic imaging and initiate corticosteroid treatment • Add prophylactic antibiotics for opportunistic infections
	Grade 3 or 4, or recurrent Grade 2	Permanently discontinue		
Diarrhea / Colitis	Grade 2 or 3	Withhold	
 • Administer corticosteroids (initial dose of 1-2 mg/kg prednisone or equivalent) followed by taper 	
 • Monitor participants for signs and symptoms of enterocolitis (ie, diarrhea, abdominal pain, blood or mucus in stool with or without fever) and of bowel perforation (ie, peritoneal signs and ileus).

	Grade 4 or recurrent Grade 3 (for =Colitis)	Permanently discontinue		
 Participants with \geq Grade 2 diarrhea suspecting colitis should consider GI consultation and performing endoscopy to rule out colitis. Participants with diarrhea/colitis should be advised to drink liberal quantities of clear fluids. If sufficient oral fluid intake is not feasible, fluid and electrolytes should be substituted via IV infusion.
AST / ALT elevation or Increased bilirubin	Grade 2	Withhold	
 Administer corticosteroids (initial dose of 0.5- 1 mg/kg prednisone or equivalent) followed by taper 	
 Monitor with liver function tests (consider weekly or more frequently until liver enzyme value returned to baseline or is stable)
	Grade 3 or 4	Permanently discontinue	
 Administer corticosteroids (initial dose of 1-2 mg/kg prednisone or equivalent) followed by taper 	
Type 1 diabetes mellitus (T1DM) or Hyperglycemia	Newly onset T1DM or Grade 3 or 4 hyperglycemia associated with evidence of β -cell failure	Withhold	
 Initiate insulin replacement therapy for participants with T1DM Administer anti-hyperglycemic in participants with hyperglycemia 	
 Monitor participants for hyperglycemia or other signs and symptoms of diabetes.
Hypophysitis	Grade 2	Withhold	
 Administer corticosteroids and initiate hormonal replacements as clinically indicated. 	
 Monitor for signs and symptoms of hypophysitis (including hypopituitarism and adrenal insufficiency)
	Grade 3 or 4	Withhold or permanently discontinue ¹		
Hyperthyroidism	Grade 2	Continue	
 Treat with non-selective beta-blockers (eg, propranolol) or thionamides as appropriate 	
 Monitor for signs and symptoms of thyroid disorders.
	Grade 3 or 4	Withhold or		

		permanently discontinue ¹		
Hypothyroidism	Grade 2-4	Continue	
 Initiate thyroid replacement hormones (eg, levothyroxine or liothyronine) per standard of care 	
 Monitor for signs and symptoms of thyroid disorders.
Nephritis and Renal dysfunction	Grade 2	Withhold	
 Administer corticosteroids (prednisone 1-2 mg/kg or equivalent) followed by taper. 	
 Monitor changes of renal function
	Grade 3 or 4	Permanently discontinue		
Myocarditis	Grade 1 or 2	Withhold	
 Based on severity of AE administer corticosteroids 	
 Ensure adequate evaluation to confirm etiology and/or exclude other causes
	Grade 3 or 4	Permanently discontinue		
All other immune-related AEs	Intolerable/persistent Grade 2	Withhold	
 Based on type and severity of AE administer corticosteroids 	
 Ensure adequate evaluation to confirm etiology and/or exclude other causes
	Grade 3	Withhold or discontinue based on the type of event. Events that require discontinuation include and not limited to: Gullain-Barre Syndrome, encephalitis		
	Grade 4 or recurrent Grade 3	Permanently discontinue		

1. Withhold or permanently discontinue pembrolizumab is at the discretion of the investigator or treating physician.
 
NOTE: For participants with Grade 3 or 4 immune-related endocrinopathy where withhold of pembrolizumab is required, pembrolizumab may be resumed when AE resolves to ≤ Grade 2 and is controlled with hormonal replacement therapy or achieved metabolic control (in case of T1DM).
				

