V4.03 CTCAE Grading	Grade 1	Mild; asymptomatic or mild symptoms; clinical or diagnostic observations only; intervention not indicated.
	Grade 2	Moderate; minimal, local or noninvasive intervention indicated; limiting age-appropriate instrumental ADL.
	Grade 3	Severe or medically significant but not immediately life-threatening; hospitalization or prolongation of hospitalization indicated; disabling; limiting self-care ADL.
	Grade 4	Life threatening consequences; urgent intervention indicated.
	Grade 5	Death related to AE
Seriousness	A serious adverse event is any adverse event occurring at any dose or during any use of Merck product that:	
	† Results in death ; or	
	† Is life threatening ; or places the participant, in the view of the investigator, at immediate risk of death from the event as it occurred (Note: This does not include an adverse event that, had it occurred in a more severe form, might have caused death.); or	
	† Results in a persistent or significant disability/incapacity (substantial disruption of one’s ability to conduct normal life functions); or	
	† Results in or prolongs an existing inpatient hospitalization (hospitalization is defined as an inpatient admission, regardless of length of stay, even if the hospitalization is a precautionary measure for continued observation. (Note: Hospitalization for an elective procedure to treat a pre-existing condition that has not worsened is not a serious adverse event. A pre-existing condition is a clinical condition that is diagnosed prior to the use of a Merck product and is documented in the patient’s medical history.); or	
	† Is a congenital anomaly/birth defect (in offspring of participant taking the product regardless of time to diagnosis);or	
	Is a new cancer (that is not a condition of the study) (although not serious per ICH definition, is reportable to the Sponsor within 24 hours and to Merck within 2 working days to meet certain local requirements); or	
	Is an overdose (whether accidental or intentional). Any adverse event associated with an overdose is considered a serious adverse event for collection purposes. An overdose that is not associated with an adverse event is considered a non-serious event of clinical interest and must be reported within 24 hours to the Sponsor and to Merck within 2 working days..	

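### In Table 7.3.2, hypophysitis that never exceeds Grade 2 has a stricter condition for resuming pembrolizumab than hypophysitis that reached Grade 3 or 4

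*Combined protocol and SAP*

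**What the plan says.** All the relevant text is in Table 7.3.2, in the section on dose modification and toxicity management for immune-related adverse events.

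- **General instruction 2, resuming.** For a withheld drug, "pembrolizumab can be resumed after AE has been reduced to Grade 1 or 0 and corticosteroid has been tapered".
- **General instruction 2, time limit.** "Pembrolizumab should be permanently discontinued if AE does not resolve within 12 weeks of last dose".
- **Hypophysitis row, Grade 2.** "Hypophysitis Grade 2 Withhold". The management cell reads "Administer corticosteroids and initiate hormonal replacements as clinically indicated".
- **Hypophysitis row, Grade 3 or 4.** "Withhold or permanently discontinue", with footnote 1: "Withhold or permanently discontinue pembrolizumab is at the discretion of the investigator or treating physician".
- **NOTE under the table.** It is limited to endocrinopathy of Grade 3 or 4 for which the drug was withheld. For those patients, "pembrolizumab may be resumed when AE resolves to ≤ Grade 2 and is controlled with hormonal replacement therapy". For type 1 diabetes (T1DM), metabolic control is the alternative condition.
- **T1DM or hyperglycemia row.** The drug is withheld for newly onset T1DM, with no grade given, or for Grade 3 or 4 hyperglycemia with evidence of beta-cell failure.
- **Myocarditis row.** The drug is withheld at Grade 1 or 2 and permanently discontinued at Grade 3 or 4.
- **Thyroid rows.** Treatment continues for hyperthyroidism at Grade 2 and for hypothyroidism at Grades 2 to 4.

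**The concern.** A table of this kind should let a site read one resume condition from the event and its grade. For hypophysitis the condition depends on the past peak grade, and it does so in an unexpected direction: the milder course meets the stricter threshold. Nothing in the table explains this as intended.

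What is at stake is patient management, and through it the safety and tolerability objectives for both cohorts (section 5.2). Sites that meet a controlled Grade 2 hypophysitis may apply the NOTE by analogy or apply instruction 2 literally. Pembrolizumab exposure would then depend on the line that was read.

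**Working it through.** The plan states no figure on this point, so the check sets the parts of the table side by side.

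**1. Hypophysitis.** Take two patients, both now at Grade 2 and both controlled on hormonal replacement. The Grade 2 management cell itself foresees replacement, so the second patient is not an artificial case.

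| | Peak Grade 3 or 4 | Peak Grade 2 |
|---|---|---|
| Action at the peak grade | Withhold or discontinue, physician's choice (suppose withheld) | Withhold |
| Rule for resuming | NOTE | General instruction 2 |
| Grade required | 2 or lower | 1 or 0 |
| Grade condition met now | Yes | No |
| 12-week limit | Not stated for NOTE patients | Applies |

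The thresholds differ by 2 − 1 = 1 grade, and the only difference between the two patients is the peak grade.

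**2. Is the mismatch general to endocrine events?** No. In the hyperthyroidism row the NOTE fits: Grade 3 or 4 may be withheld, and Grade 2 is a grade at which treatment continues. Hypothyroidism continues throughout Grades 2 to 4. The mismatch arises where a row withholds at Grade 2. Among the named endocrine rows that is hypophysitis. An endocrine event without its own row could show the same pattern under the row for all other immune-related events, if an intolerable or persistent Grade 2 event and a Grade 3 event were both withheld.

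**3. T1DM.** The first part of the row's condition carries no grade, so newly onset T1DM below Grade 3 is withheld as written. The metabolic-control route in the NOTE is worded for Grade 3 or 4. The table does not say which resume condition applies below Grade 3. On the wording alone it is instruction 2.

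**4. Myocarditis.** The pneumonitis, colitis, hepatic and renal rows withhold from Grade 2 upward, so resuming at Grade 1 or 0 does not overlap with them. Myocarditis is the only named row that withholds at Grade 1. Instruction 2 speaks of an event that has been reduced. An event that fell from Grade 2 to Grade 1 meets its grade condition. For an event that began at Grade 1 there are two readings: it already sits at the resume grade, or it has to reach Grade 0.

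**5. Does another section settle it?** No. Section 7.6.3 sends the reader to Table 7.3.3 for managing immune-related events, and section 7.7 cites section 7.3.3 for unacceptable adverse experiences. Both lead to the guidance on infusion reactions. Footnote 1 gives discretion over withholding or discontinuing at Grade 3 or 4, not over resuming after Grade 2.

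**6. Scale.** Twelve weeks at one dose every 3 weeks is 12 / 3 = 4 scheduled doses. One patient is 1/20 = 5 percentage points of cohort P and 1/34 = 2.9 points of cohort D at full enrolment. The plan says only that adverse events will be reported as proportions and names no discontinuation proportion, so these figures give scale and not an effect on a planned result.

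**The case against.** The best defence is that withholding and resuming are successive steps. The rows say what to do when an event is graded; instruction 2 and the NOTE say when a withheld drug may restart. The NOTE is then a specific exception to a general rule, with an added condition of hormonal control. That stands in part: a patient who resumes at Grade 2 under the NOTE does not contradict the row merely because the row withholds at Grade 2. It does not explain why an equally controlled event that peaked at Grade 2 has no such exception.

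A reader might infer more than the text supports:

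- **That the two patients receive opposite orders.** Resumption is permissive and conditional in both places, and Grade 3 or 4 hypophysitis may also be permanently discontinued at the physician's discretion. What differs is the resume threshold.
- **That after 12 weeks the milder case stops for good while the more severe case continues.** The NOTE relaxes the grade and is silent on the time limit. It does not exempt its patients.
- **That a patient on replacement or insulin can never reach Grade 1.** Table 9.2 describes Grade 1 as "clinical or diagnostic observations only; intervention not indicated", but that is the generic descriptor. Events are graded by CTCAE 4.03, whose event-specific definitions the protocol does not reproduce.
- **That every Grade 2 endocrine event is held to the stricter rule.** Both thyroid rows say otherwise.
- **That the myocarditis row and instruction 2 plainly conflict.** On the ordinary sense of a reduction, an event that began at Grade 1 has not been reduced to Grade 1. This is an ambiguity.

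**Conclusion.** The hypophysitis inconsistency is in the text and no other section removes it. The milder course has a resume threshold one grade stricter than the more severe course, for patients at the same controlled grade. Whether the 12-week limit applies under the NOTE is left open. The T1DM and Myocarditis rows each contain a lesser ambiguity of the same kind.

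This rests on two readings of the table: that the NOTE covers Grade 3 or 4 hypophysitis when the physician chooses to withhold, and that general instruction 2 governs any withheld event outside the NOTE. Both follow the wording.

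How often it will matter cannot be estimated. The documents give no rate for hypophysitis that peaks at Grade 2 and stays above Grade 1, and a rate for all endocrine and cardiac immune events together would overstate it. No sample size, error rate or ORR figure is affected. The point should be corrected because it concerns patient safety and the correction is simple.

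**What to change.** Reconcile general instruction 2, the Hypophysitis, T1DM and Myocarditis rows and the NOTE so that each event and grade carries one resume condition. The revised table should state:

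1. which condition applies to hypophysitis that never exceeded Grade 2 and is controlled on replacement;
2. which condition applies to newly onset T1DM below Grade 3;
3. which condition applies to myocarditis that began at Grade 1;
4. whether the 12-week limit applies to events under the NOTE.

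Which clinical rule to adopt in each case is for the sponsor's medical team; this review takes no position on it. The cost is a wording change to one table by protocol amendment. No extra patients, visits or procedures are needed.
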